ramifications given the prevalence, frequent treatment resistance, and chronicity characteristic of LLD. Even apart from patients with LLD, cognitive and motor slowing exact a large public health burden in terms of impaired functioning and increased morbidity and mortality, and this burden will only grow as the population ages. It is critical to develop treatments capable of altering the negative health trajectories associated with slowing in order to help older adults maintain independent functioning and live longer with an increased quality of life. Finally, while PET and MRI may prove critical to understand the neurobiology of slowing and LLD, their invasiveness and expense limit their roles in informing treatment decisions in clinical practice settings. For this reason we are also assessing the influence of genetic moderators such as interleukin-6 (IL-6) and catechol-O-methyl-transferase (COMT) genotype on baseline dopamine functioning and response to L-DOPA. This may facilitate the identification of both high-risk individuals and those most likely to benefit from treatment interventions.

Specific Aims and Hypotheses

Specific Aims and Hypotheses

We hypothesize that treatment with levodopa (L-DOPA) will improve depressive symptoms in LLD by enhancing striatal dopamine release and improving cognitive/motor slowing. In the R61 Phase, 60 adults aged > 60 years with (1) a DSM 5 depressive disorder, (2) significant depressive symptoms (CES-D > 10), (3) decreased processing speed (1 SD below age-adjusted norms on the Digit Symbol Test) and decreased gait speed (average walking speed over 15' course < 1m/s) will be receive 3 weeks of treatment with L-DOPA up to 450mg. A 300mg test dose will be tested for engagement of molecular target by determining whether L-DOPA displaces [11C]-raclopride on positron emission tomography (PET). If L-DOPA increases dopamine release and improves slowing at our proposed thresholds, we will proceed to compare the dose of L-DOPA exhibiting optimal target engagement to placebo in a subsequent R33 Phase.

R61 Phase.

Aim 1: To determine whether L-DOPA administration increases dopamine release.

Hypothesis 1: 300mg L-DOPA will reduce [11C]-raclopride binding potential (BP) in the caudate and putamen.

Aim 2: To determine whether L-DOPA increases processing and gait speed in depressed older adults.

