- 6. Half of the total sample will undergo neuroimaging (N=30 of total N=60). Subjects will undergo a pretreatment MRI and PET scan and a post-treatment MRI and PET scan (i.e., 2 total MRIs, 2 total PET scans, separated by the 3 week clinical trial). Subjects who do not meet imaging selection criteria or who do not wish to undergo scanning will be allowed to participate in the clinical trial portion of the study only. MRI and PET scanning may occur on the same day if this can be scheduled (MRI occurring first, followed by PET scan). However, due to the tightness of scheduling for these scanners, it is more likely that the MRI and PET scans will occur on different days--one day for MRI scan and one day for the PET scan. Typically the MRI scanning day will come before the PET scanning day.
- 7. MRI of the brain will be acquired using a GE MR750 3.0T System. At the start of the session, a 3-Plane localizer (scout) will be acquired to determine patient position. Subjects will then receive T1-weighted 3D SPGR (Spoiled Gradient Echo), T2 FLAIR, and EPI scans. Acquisition parameters for the EPI scans will be: TE/TR (ms) 20/2000; Flip Angle (deg) 720; in-plane resolution (voxels) 112x112; slice thickness/gap (mm) 3/0; slices 41.

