- 8. For the MRI procedures, participants are instructed to lie as still as possible within the magnet. The MRI scan is completed in one session, and lasts for a total of 60 minutes. All precautions and protections are given to the participant to ensure that they are as safe and as comfortable as possible. For participants' comfort within the scanner, they lie on a padded table with a pillow to rest their heads on. A blanket is also provided to keep participants warm during the procedure. If the participant appears nervous or anxious, a trained member of the research staff remains with them inside the scanning suite for the duration of the scan. The participant is given a squeeze ball to terminate the scan at any time. If he/she squeezes the ball, he/she will be removed from the scanner immediately. Participants may decline the MRI scans at any time. If the participant chooses not to be scanned, his/her participation in the study will not be affected. Of course, a structural MRI scan would be required to participate in the PET scans. Any subject who cannot have at least a structural MRI scan would not be able to participate in this protocol. All of the MRI procedures are conducted on the 3-Tesla MRI scanner at the New York State Psychiatric Institute. Conducting these procedures will be an accredited Magnetic Resonance Technologist and one member of the research staff (Bachelor's Level or Higher), or [name] or [name], present.

PET Scanning

9. The neuroimaging subset of depressed subjects will have 2 [11C]-raclopride PET scans: (1) pre-treatment and (2) post-treatment (at the end of the 3 week duration trial).

- 10. PET experiments will be conducted with the mCT scanner in the PET Suite on the R1 level of the Public Health Building. Subjects participating in the study will be escorted on PET scan day by a research staff member to the R1 level of the Public Health Building where the PET scanner is located. A research staff person will stay with the subject at all times throughout the procedure and during transportation to and from the PET Center. The preparation of the subject will include the placement of a venous catheter.

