- 13. Post-treatment scan: As close to the end of the 3 week study as possible (based on PET scheduling), subjects will undergo their post treatment scan. We will follow standard procedures for measuring L-DOPA-induced changes in synaptic dopamine levels set forth in PET studies of PD patients. Subjects will be given 75mg carbidopa/300mg L-DOPA approximately 1.5 hours before scanning. Subjects in week 3 of the protocol are taking 450mg LDOPA per day (150mg three times daily), so the 300mg administered prior to the post-treatment PET scan will constitute 300mg of their usual 450mg daily dose on the scan day. A low dose CT transmission scan is obtained prior to intravenous administration of 14mCi [11C] raclopride (or less). The start of tracer injection will be timed to coincide with the time of onset of L-DOPA effects (approximately 60-90 minutes following oral dose). Thus, the 60 minute PET scanning session will occur from 90 minutes to 150 minutes following L-DOPA dosing in all subjects. At the completion of the scan the IV catheter will be removed, and the subject will be evaluated (including mental status and vital signs) by a study physician. Vital signs, and physical exam will be performed prior to discharge from the PET suite.
- 14. We are aware that the scanning dose of 300mg given at once approximates but may not match the CNS effects of subchronic dosing with 150mg tid. However, this method has the advantages of being consistent with imaging studies of PD patients in which L-DOPA doses are typically 250-300mg and avoiding confounding of Δ BPND estimates by downregulation of D2 receptors occurring with subchronic administration. Since nausea is a known side effect of L-DOPA, we will be particularly vigilant about monitoring for it. When nausea occurs patients generally feel warm and sick to their stomachs. It will likely

occur after PET scanning, but if vomiting were necessary, the MD would remove the subject from the scanner so that vomiting does not occur while supine. Removal from the scanner can occur immediately.

- 15. PET data will be reconstructed into images using the appropriate reconstruction protocols and filters. PET images will be coregistered to the MRI and regional time activity curves will be measured. Data will be fitted to pharmacokinetic models, and relevant pharmacokinetic parameters, including the percent of receptors engaged by dopamine, will be estimated based on the model fitting procedures.

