- 16. Drs. [name] and [name] continue to be Co-Investigators responsible for neuroimaging as part of a subcontract executed between RFMH and SUNY-Stony Brook. They will lead analyses of neuroimaging data. In terms of on-site execution of PET and MRI scans, these are supervised by the study PI ([name]) and/or [name], who works with the Aging Program as a study clinician and has a research background in PET neuroimaging.

Clinical treatment

- 16. An effort will be made for all subjects to be titrated up to 450mg L-DOPA over a 3 week-duration study. We chose 450mg as the target dose because it is higher than doses known to affect cognition (i.e., 150-300mg) but lower than levels used for PD (i.e., 600-1200mg) that may have greater side effects. Each subject will start taking 37.5mg carbidopa/150 mg levodopa (1.5 25/100 sinemet tablets) once daily for one week, then increase to 75mg carbidopa/300mg levodopa (1.5 25/100 sinemet tablets twice daily) for one week, and finally increase to 112.5mg carbidopa/450mg levodopa (1.5 25/100 sinemet tablets three times daily) for one week. Each subject will be titrated to 450mg L-DOPA unless they cannot tolerate higher doses, in which case subjects will have their dosage reduced to the maximum tolerable dose.
- 17. Although each subject is titrated up to 450mg L-DOPA if it is tolerated, the study design allows us to assess the effects and tolerability of three different L-DOPA doses (150mg, 300mg, and 450mg). Based on published work using L-DOPA for PD, we expect effects on cognition and gait to be apparent at each dosing level approximately 5 days after dosage increases. By performing assessments weekly, we will thus obtain measures of L-DOPA's effect on processing and gait speed at each dosing level. We carefully reviewed the literature and consulted our Co-Investigator [name] (neurologist and PD expert) for evidence of carry-over effects of L-DOPA dosing (such that prior experience with 150mg and 300mg may influence a subject's experience of receiving 450mg). We found little evidence to suggest there are significant carry-over effects from previous L-DOPA doses, so each dose will be able to be assessed on its own merits. Similarly, we do not anticipate that the repeated assessments of processing and gait speeds will bias the study results.

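### PET item 14 claims to avoid confounding by D2 down-regulation, but the only contrast compares an untreated scan with one taken after about three weeks of daily L-DOPA

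*Combined protocol and SAP*

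**What the plan says.** Under PET Scanning, item 14 concedes that 300 mg given at once may not reproduce the effect of 150 mg three times daily. It then lists two advantages of the method: consistency with imaging studies in Parkinson's disease, and avoiding confounding of ΔBPND "estimates by downregulation of D2 receptors occurring with subchronic administration".

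The schedule is given in nearby items:

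- MRI Scanning, item 6: "2 total MRIs, 2 total PET scans, separated by the 3 week clinical trial". PET Scanning, item 9 repeats the pre-treatment and end-of-treatment timing.
- PET Scanning, item 12 describes the baseline scan with no L-DOPA.
- PET Scanning, item 13 places the second scan as near the end of the three weeks as scheduling allows. The 300 mg scan dose "will constitute 300mg of their usual 450mg daily dose on the scan day".
- Clinical treatment, item 16 has weekly steps of 150, 300 and 450 mg/day: "Each subject will be titrated to 450mg L-DOPA unless they cannot tolerate higher doses".

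Specific Aims and Hypotheses presents the scan as an acute test: "A 300mg test dose will be tested for engagement of molecular target by determining whether L-DOPA displaces" raclopride. Aim 1 asks whether L-DOPA increases dopamine release. Increased release is one of two conditions for moving to the R33 phase; improved slowing is the other. The closing sentence of Summary of Experiences to Date credits the results, including the fall in raclopride binding, to greater dopamine availability.

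**The concern.** The protocol itself names D2 down-regulation as a confounder of ΔBPND and ties it to subchronic dosing. It then takes its only on-drug scan after subchronic dosing and compares it with a scan before any dosing. The method changes how much dopamine is present during the second scan. It does not undo the preceding weeks of treatment.

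The error would run in the favourable direction. Fewer D2 receptors and more dopamine both reduce raclopride binding, so any receptor loss would be read as release. That bears on Aim 1, on the molecular half of the R33 condition, and on the mechanism stated in the progress summary. The results for processing speed, gait speed and HRSD do not depend on it.

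**Working it through.** **Scans and exposure**

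| Scan | L-DOPA before scan day | L-DOPA on scan day |
|---|---|---|
| Pre-treatment (items 9, 12) | none in the trial | none |
| Post-treatment (items 9, 13) | about 3 weeks, daily | 300 mg about 1.5 h before scanning |

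Both columns change between the rows, so one contrast carries two unknowns.

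**Exposure before the second scan.** Assume 7-day steps, full adherence and a scan on days 15 to 21, giving 14 to 20 prior dosing days.

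- Fully titrated, day 15: 7×150 + 7×300 = 3,150 mg.
- Fully titrated, day 21: 7×150 + 7×300 + 6×450 = 5,850 mg.
- Held at 150 mg/day: 14×150 = 2,100 mg to 20×150 = 3,000 mg.
- Scan dose as a share of all L-DOPA taken by then, fully titrated: 300/(3,150 + 300) = 8.7% down to 300/(5,850 + 300) = 4.9%.
- If the scan follows 21 complete days, prior exposure is 3,150 + 7×450 = 6,300 mg.

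These figures show that the second scan is taken in a subchronically dosed state. They do not measure receptor loss, because the documents give no relation between cumulative dose and D2 density.

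**Why the contrast cannot separate the two effects (illustration only).** Take BPND as proportional to receptor density times the fraction not displaced, with affinity unchanged. With receptor loss L and displacement d, the observed fall is f = 1 − (1 − L)(1 − d), so d = 1 − (1 − f)/(1 − L). The documents report no percentage change in BPND, so f is assumed.

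| Assumed fall f | Receptor loss L | Implied displacement d |
|---|---|---|
| 5% | 0 / 2.5% / 5% | 5.0% / 2.6% / 0 |
| 10% | 0 / 5% / 10% | 10.0% / 5.3% / 0 |
| 15% | 0 / 7.5% / 15% | 15.0% / 8.1% / 0 |

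Within each row, all three combinations give the same pair of scans.

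**Reported PET results.** From Summary of Experiences to Date, df = 24, so n = 25 and mean/SD = t/√25.

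- Sensorimotor: t = −4.85, giving −0.97 SD, p = 0.00006.
- Associative: t = −2.52, giving −0.50 SD, p = 0.019.
- Limbic: t = 0.265, giving +0.05 SD, p = 0.793. The 95% CI is 0.053 ± 2.064/5, or −0.36 to +0.47 SD.

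The p-values agree with those reported. They show that binding changed in two regions, not why.

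**Does anything else close the gap?**

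- No washout, first-dose scan, off-drug post-treatment scan or untreated imaging group is described.
- Item 15 lists model outputs, "including the percent of receptors engaged by dopamine, will be estimated based on the model fitting procedures", but names no model and does not say how occupancy would be separated from receptor density.
- Clinical treatment, item 17 says "We found little evidence to suggest there are significant carry-over effects from previous L-DOPA doses", but this concerns how earlier doses affect the experience of later ones, not receptor density.
- The Statistical Analysis plan does not mention PET.

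**The case against.** The strongest reply is that the method in item 14 means only the single 300 mg dose, chosen over scanning on routine three-times-daily dosing. The sentence would then be an overstated relative advantage, not a claim that the before-and-after contrast isolates release. That reading is fair, but the word avoiding is still wrong on it, because the subject has had weeks of dosing either way.

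Second, the progress summary mostly reports the PET findings neutrally, as changes in binding, and nowhere says that acute release is the sole cause. This is true, but its last sentence does assign the mechanism to dopamine availability, and Aim 1 is framed as release.

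Third, the regional pattern is internal evidence. A flat limbic result beside falls elsewhere argues against loss uniform across the striatum. That stands, but it does not exclude loss confined to the regions where binding fell.

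Fourth, the reference list includes a simplified reference tissue model (reference 128). Item 15 does not cite it, and a listing shows neither that it was used nor that it separates the two effects.

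Finally, interventions are complete and the R33 thresholds are not in these documents, so the practical consequence may be limited. That is why the remedy is confined to wording.

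**Conclusion.** The concern holds. The design does not have the property item 14 claims for it: it cannot exclude the confounder the protocol names. The conclusion rests on the scan schedule and on the protocol's own premise that down-regulation occurs with subchronic dosing. It does not rest on any estimate of how much occurred.

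The size of any bias is unknown. Under the simple model, anything from none to all of the observed fall could be receptor loss. The documents do not show that down-regulation took place. The test of a fall in binding potential in Hypothesis 1 stands as a test of net change. What lacks support is reading that fall as dopamine release alone. The slowing half of the R33 condition is unaffected, and the documents do not show whether the R33 decision is still open.

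**What to change.** - Delete the claim in item 14 that confounding is avoided, or reconcile it with items 9 and 13. If the protocol text is left unchanged as a record of what was planned, state the limitation wherever Aim 1 is reported.
- Report Aim 1, including the closing sentence of the progress summary, as a net change in D2 availability after about three weeks of L-DOPA plus the 300 mg scan dose, which may reflect dopamine release, receptor down-regulation or both.
- Attach the same caveat to item 15's estimate of receptor engagement by dopamine, unless the model used is named and shown to separate the two.
- Do not treat this contrast alone as proof of the dopamine-release half of the R33 condition.

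This costs wording only. It needs no new scans, data or analyses, and it is still possible because only data analysis is ongoing. The price is a weaker mechanistic claim for Aim 1.

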I am submitting an annual continuation without modifications

Division & Personnel

Division

What Division/Department does the PI belong to?

Psychiatry

Within the division/department, what Center or group are you affiliated with, if any? program on healthy aging and late life brain disorders

Unaffiliated Personnel

List investigators, if any, who will be participating in this protocol but are not affiliated with New York State Psychiatric Institute or Columbia University. Provide: Full Name, Degrees and Affiliation.

[name] (SUNY Stony Brook)

[name] (SUNY Stony Brook)

Application for Continuation of Research

Status

Current Status of Study:

All research interventions were completed. Only data analysis is ongoing.

Summary of Experiences to Date

Please provide a summary of scientific progress of the study and the experience of research participants, to date. This requirement is designed to allow for the investigator and the IRB to reassess the study's risks and benefits in terms of developments in the field, changing practice patterns, and new IRB policies and procedures.

36 subjects participated who were 75.3 ± 7.5 years old and 44.4% male. Significant, dose dependent increases in processing and gait speed were observed with L-DOPA (450mg dose: processing speed factor score effect size [ES] = 0.41, p = 0.001; dual task gait speed ES = 0.43, p = 0.003). [11C]raclopride Δ BPND was significantly different from 0 in sensorimotor (t = -4.85, df = 24, p < 0.001) and associative striatum (t = -2.52, df 24, p = 0.019) but not in limbic striatum (t = 0.265, df = 24, p = 0.793). Depressive symptoms decreased significantly on the Hamilton Rating Scale for Depression (ES = -0.4, p = 0.01). Drop-out rate was 8.3%, and nausea was the most frequently-reported side effect. By enhancing availability of dopamine, L-DOPA improved processing and gait speed in depressed older adults and significantly decreased [11C]raclopride binding in selected striatal subregions.

Funding

Have there been any changes in funding status since the prior approval?

No

Have the principal investigator and other investigators made all required disclosures of financial interest in the study sponsor/product?

Yes

Summary

Have there been any study findings, recent literature, or untoward events occurring here or at other sites in the past year which might affect the analysis of the safety, risks or benefits of study participation? No

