Hypothesis 2: 150mg, 300mg, and 450mg L-DOPA will increase processing and gait speed, with greatest improvement occurring at the 450mg dosage level.

Exploratory aims: To obtain information on the dosing and tolerability of L-DOPA in our patient population as well as identify PET and MRI biomarkers associated with slowing.

Description of Subject Population

Sample #1

Specify subject population

adults aged >59 years with a depressive disorder, decreased processing speed, and decreased gait speed Number of completers required to accomplish study aims

48

Projected number of subjects who will be enrolled to obtain required number of completers

Age range of subject population 60 years or older

Gender, Racial and Ethnic Breakdown

On the basis of previous depression studies conducted in the Adult and Late Life Depression Research Clinic, it is anticipated that the sample will be composed of 60% women and 40% men as well as approximately 75% Caucasian, 15% African American, and 10% Hispanic subjects.

On the basis of previous depression studies conducted in the Adult and Late Life Depression Research Clinic, it is anticipated that the sample will be composed of 60% women and 40% men. Description of subject population

This phase will enroll 60 outpatients who (1) are aged \geq 60 years, (2) diagnosed with Diagnostic and Statistical Manual (DSM) 5 (107) MDD, Dysthymia, or Depression Not Otherwise Specified (NOS), (3) have Center for Epidemiologic Studies-Depression Rating scale (CES-D) (108) score \geq 10, (4) have decreased gait speed (defined as average walking speed over 15' course \leq 1m/s), and (5) are willing to and capable of providing informed consent and complying with study procedures.

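### Weekly visits are read as dose levels although doses may be reduced, so the 450 mg effect belongs to no defined dose or fixed set of subjects

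*Combined protocol and SAP*

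**What the plan says.** Study Procedures, Clinical treatment, item 16 sets one dose per week: 150 mg, then 300 mg, then 450 mg. The target is qualified: "An effort will be made for all subjects to be titrated up to 450mg L-DOPA over a 3 week-duration study". Subjects who cannot tolerate higher doses are the exception, "in which case subjects will have their dosage reduced to the maximum tolerable dose".

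Item 17 opens with the same qualifier, speaking of all three dose levels: "Although each subject is titrated up to 450mg L-DOPA if it is tolerated, the study design allows us to assess the effects and tolerability". It then draws the inference at issue: "By performing assessments weekly, we will thus obtain measures of L-DOPA's effect on processing and gait speed at each dosing level". It adds that each dose can be judged separately. PET Scanning item 13 makes the same equation without a qualifier: "Subjects in week 3 of the protocol are taking 450mg LDOPA per day (150mg three times daily".

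Two other sections bear on who is measured at what dose. Criteria for Early Discontinuation withdraws subjects who develop significant side effects or an adverse event. The L-DOPA risk section repeats the allowance for reduction and withdraws subjects who cannot tolerate 150 mg daily.

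Hypothesis 2 expects gains at all three doses, "with greatest improvement occurring at the 450mg dosage level". Summary of Experiences to Date reports dose-dependent gains and gives "450mg dose: processing speed factor score effect size [ES] = 0.41, p = 0.001; dual task gait speed ES = 0.43, p = 0.003", with no number of subjects on 450 mg. The Statistical Analysis plan names chi-square and independent-samples t-tests for the dose-dependent gains. It does not say whether 450 mg means the Week 3 visit or the dose taken, who is in that set, or how reduced or withdrawn subjects are handled.

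**The concern.** Week and dose coincide only for subjects who move up on schedule. Once someone is reduced, the analyst has two options. Grouping by week puts lower-dose values under the 450 mg label. Grouping by dose taken leaves only those who tolerated 450 mg. Withdrawal for side effects adds to that selection under either option, because withdrawn subjects may contribute to the early visits and not to Week 3.

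The dose ordering is what is at stake. If the 150 and 300 mg means come from more people than the 450 mg mean, a rise across doses can appear, or a real one can be masked, without any corresponding change within a person. Independent-samples t-tests do not guard against this, because they do not hold the subjects constant across doses. The problem is separate from practice or time effects and would remain if there were none.

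**Working it through.** **Inputs.** From Summary of Experiences to Date: 36 participants; 8.3% drop-out; ES 0.41 (p = 0.001) for processing speed and 0.43 (p = 0.003) for dual-task gait at 450 mg. The share below 450 mg at Week 3 is not given; I assume f = 10%, 20% or 30%. The effect in reduced subjects is not given; I assume d = 0.2, with d = 0 as a harsher case.

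**Step 1: can the reported figures be reproduced?** The drop-out rate can: 3/36 = 8.3%. It counts drop-outs and says nothing about dose reductions. The effect sizes cannot, since no n or SD is given. Nor can the n be recovered from ES and p:
- If ES is the mean change divided by the SD of the change, t = ES × √n. Two-sided p = 0.001 at ES 0.41 then needs about 71 subjects, and p = 0.003 at ES 0.43 about 53. Only 36 took part.
- If ES is scaled by the baseline SD, t = ES × √n / √(2(1 − r)), with r the pre-post correlation. Any n from 20 to 36 then fits, with r from 0.89 down to 0.77 for processing speed and from 0.84 down to 0.67 for gait.

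So the figures do not reveal whether 450 mg means everyone at Week 3 or only those on 450 mg.

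**Step 2: size if the reported ES came from tolerators only.** The Week 3 effect in all assessed is ES × (1 − f) + d × f, assuming the same outcome SD in both subgroups.

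| f | ES 0.41, d = 0.2 | ES 0.41, d = 0 | ES 0.43, d = 0.2 | ES 0.43, d = 0 |
|---|---|---|---|---|
| 10% | 0.389 | 0.369 | 0.407 | 0.387 |
| 20% | 0.368 | 0.328 | 0.384 | 0.344 |
| 30% | 0.347 | 0.287 | 0.361 | 0.301 |

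For example, 0.41 × 0.8 + 0.2 × 0.2 = 0.328 + 0.040 = 0.368. If Week 3 was used for everyone, the reported value already is this mixture, and only its label needs changing.

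**Step 3: effect on the dose ordering.** Suppose all subjects are measured at 300 mg and only tolerators at 450 mg. Let T be the tolerators' gain and N the non-tolerators' gain. The apparent step is

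T450 − [(1 − f) × T300 + f × N300] = (T450 − T300) + f × (T300 − N300).

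The first term is the within-person step. The second comes only from the change in who is measured: it is positive if tolerators gain more at 300 mg and negative if they gain less. With no within-person step, T = 0.41 at both doses and N = 0 (assumed), the means would appear to rise from 0.369 to 0.41 (f = 10%), 0.328 to 0.41 (20%) or 0.287 to 0.41 (30%).

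**The case against.** The strongest reply is that the plan knows some subjects may not reach 450 mg. Item 17 says so, the Lay Summary and Specific Aims speak of treatment up to 450 mg, tolerability is an exploratory aim, and pill counts are taken weekly. This stands: the plan recognises the issue but has no analysis rule to match. It does not rescue the inference in item 17, which fails as soon as one subject is reduced.

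The size is also hypothetical. The number reduced could be zero, and the d = 0 column sits badly with Hypothesis 2, which expects benefit at the lower doses. With d = 0.2 the processing-speed shift is about 0.02 to 0.06. If about 33 were analysed (36 less the 3 drop-outs) and ES and p come from the same t-type test, the 95% interval around 0.41 is roughly 0.18 to 0.64, and every processing-speed value in the table lies inside it. That limits the practical weight of the point. It does not settle what the 450 mg result describes.

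Three stronger readings are tempting and are not supported:
- A reader might infer that the result misdescribes a regimen to be carried into R33 with intolerant subjects included. The Lay Summary carries forward the dose best tolerated, the Specific Aims the dose with the best target engagement, and R33 falls under a separate IRB protocol.
- A reader might infer that reduced subjects were measured too soon, from item 17's remark about five days. That remark concerns dose increases only.
- A reader might take the mismatch between ES, p and 36 subjects under the first scaling as an error. A different scaling explains it.

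**Conclusion.** The point holds as a defect in how the dose-level result is defined. Items 16 and 17 and PET item 13 cannot all be followed literally once a subject is reduced, and the Statistical Analysis plan does not choose between the two readings. The reported 450 mg effects and the dose-dependent pattern therefore cannot be assigned to a dose or to a fixed set of people.

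The documents do not show that the reported effects are inflated or that the dose gradient is an artefact. If nobody was reduced or withdrawn for intolerance, the problem vanishes. If Week 3 was used for everyone, the label is what is wrong. If tolerators alone were used, 0.41 would become 0.39 to 0.35, on the assumptions of 10% to 30% reduced, ES 0.2 in those subjects and equal SDs. The correction is worth making because the dose ordering is a stated hypothesis and the remedy is cheap.

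**What to change.** Replace the item 17 inference, reconcile the unqualified Week 3 statement in PET item 13 with item 16, and add to the Statistical Analysis plan:

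1. Report the Week 0 to Week 3 change in all subjects assessed at Week 3, whatever their dose, labelled *titration up to 450 mg*.
2. State the number of subjects at each actual dose at each visit, including any intermediate dose, and the number withdrawn before Week 3 with reasons. Item 1 alone would still omit those withdrawn for side effects, so add a sensitivity analysis that includes them through their available visits, for example a mixed model for repeated measures with visit as a factor.
3. Report the 450 mg result separately as *subjects who took 450 mg*. Compare it with the 150 and 300 mg results of those same subjects in a within-subject analysis, instead of independent-samples t-tests.

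The cost is one re-run from existing pill-count and dose records, some relabelling, and possibly a slightly smaller headline effect. The study status is that only data analysis remains, so this can still be done. No dosing or withdrawal rule is changed.
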